1. Care coordination. Beginning with initial enrollment, the prevention nurse will coordinate blood pressure and cholesterol management for all participants in the intervention arm. Care coordination will consist of tailored discussions with the participant and his/her providers about which provider will take primary responsibility for BP and cholesterol management. Considerations of patient-provider trust and provider comfort level or experience will inform this decision. The prevention nurse will direct subsequent management decisions to the designated provider but will facilitate communication by notifying the non-designated of any changes to medications.

At the baseline visit, the prevention nurse will map the participant's care team and communication preferences, to ensure that all providers in the patient's care team are accounted for. After the initial visit, the nurse will contact members of the participant's care team through normal clinical communication channels which are standard of care for that clinic site (e.g. EMR messages, email, phone) to inform them that the participant has been enrolled in the study. The prevention nurse may use this opportunity to discuss any potential modification to suggested blood pressure and cholesterol targets.

In order to better incorporate the prevention nurse into clinic workflow, a number of recommendations were made by the design teams. These include having nurse meet & greet and regular staff updates on the study to ensure that communication preferences are respected.

Component 1—Relevant process evaluation data for aim 3: (1) number and duration of telephone calls and emails to providers or providers' staff; (2) number and nature of communication notes

in EMR; (3) prevention nurse trust & communication ties with providers; (4) time spent coordinating care.

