2. Nurse-managed medication protocols and adherence support. Participants with BP or non-HDL above goal will receive tailored medication management and adherence support. Algorithm-based care to reduce practice variation and clinical inertia has long been recommended to assure that patients are not “stuck” at sub-therapeutic doses of medications⁸². A meta-analysis of nurse and pharmacist-led cholesterol medication adherence interventions showed substantial improvements in adherence and 15-20mg/dL reductions in total cholesterol⁴². By using algorithms and clear decision rules to guide medication titration, the prevention nurse will make recommendations to providers to improve care by reducing clinical inertia, reducing variation, and allowing non-physician staff members to assist in care. A clear and complete algorithm will also help simplify the medical regimen and emphasize medications that are affordable, effective, and have low side-effect profiles.

[figure not shown]
At each visit (in-person or telephone) where recent home BP values (average weekly BP based on a minimum of three values) exceed 130/90mmHg (in line with 2017 ACC/AHA hypertension guidelines), the prevention nurse will review the medication list with the patient, including any recent medication regimen changes and potential side-effects of each medication⁸³. The nurse will provide counseling in several areas, including ways to enhance medication adherence and prevent or ameliorate side effects. For example, patients may be given a personalized medication schedule that shows when they should take their medications.

The prevention nurse will use the algorithms described below to decide on appropriate recommendations for medication changes and will approach the designated responsible provider (HIV, PCP, or non-HIV specialist) for prescriptions and lab orders. *The responsible provider will ultimately decide on final management decisions and may request to have the participant be taken OFF management protocols as clinically indicated (e.g. recent ASCVD events or advanced CKD), in which case the participant would continue all other components of the EXTRA-CVD intervention.*

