Other medication side effects: All medications have potential side effects. Medications used in the nurse-managed protocols will be only be recommended by the nurse and must ultimately be prescribed by the subject's treating provider according to his/her best clinical judgement and approval. Common side effects of anti-hypertensive and lipid-lowering medication include but are not limited to: bradycardia, lightheadedness and orthostatic hypotension, lower extremity edema, kidney injury and electrolyte imbalances (see above), and myalgias. Rhabdomyolysis, glucose intolerance, and hepatic injury are rare complications of statin therapy.

Physical activity. All subjects will be encouraged to increase their physical activity, raising the possibility of musculoskeletal injury or unmasking of ischemic heart disease. Risks from increased physical activity will be minimized by encouraging moderate rather than vigorous activity. Providers will respond to these patient problems per usual medical practice.

Smoking. While not a key component of the intervention, all subjects will be encouraged to quit smoking (if currently using), raising the possibility of withdrawal symptoms from nicotine dependence.

Psychological risks. We do not anticipate any substantial psychological risks to be associated with participation in this study. As part of our assessments, we will ask participants about their demographic characteristics (i.e., race/ethnicity, socioeconomic status). It is possible that some participants may feel uncomfortable answering some of these questions. We will only ask questions that involve data that are important for study outcomes, and we will inform patients that they may refuse to answer any interview or survey questions, but still be involved in the study. It is also possible that participants may be uncomfortable talking with the Prevention Nurse about some topics that are included in patient-based intervention.

Protections against risk

The specific risk of participation are noted above; procedures for protection follow.

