Blood Pressure: All participants will have a high risk for CVD, and thus many will be prescribed hypertension medications by their health care provider at the outset of the study. It is likely that as a result of increased monitoring, we will detect more episodes of abnormal BP values. Because of potential high and low BP values, subjects in the intervention arm may have their current hypertension regimen adjusted. Safety monitoring of BP will occur in the context of home BP monitoring as well as BP measurement during data collection visits. An average SBP at any study visit or during home blood pressure monitoring > 180 mm Hg and/or diastolic is > 110 mm Hg will be considered an alert value and will trigger assessment by the clinician. Furthermore, an average at any study visit or during a home blood pressure monitoring that is < 90 systolic or < 40 diastolic would also be considered an alert value and would trigger an assessment by a clinician. Participants who have an alert reading at home will be asked to contact the clinician directly so that she/he can assess for any cardiovascular symptoms.

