Participants who have an alert BP reading during study visits will be directly assessed for cardiovascular symptoms during the visit. Once an alert value has been confirmed the participant will be triaged according to follow-up recommendations from Joint National Committee Recommendations (JNC 8). Participants will have access to their regular providers as well as the following study investigators designated as the clinical contact for each site: [name] (infectious disease physician and HIV clinic director; UH Special Immunology Unit), [name] (infectious disease physician and HIV clinic director; MetroHealth Medical Center) and [name] (infectious disease physician; Duke Health). If at any time, participants have symptoms of acute end organ damage (i.e. current chest pain, dyspnea at rest, new onset of blurry vision, or new neurological deficits consistent with a stroke) in the context of an elevated BP measurement (SBP > 180 , and/or DBP > 110), participants will be asked to contact the clinician and will be advised and assisted in seeking emergency medical care. For participants in the intervention group whose average SBP > 180 and DBP > 110 or SBP < 90 or DBP < 40 but are without acute symptoms, the participant's primary provider will be notified and medications will be changed as deemed appropriate by the study team. Follow up contact with the study staff will occur within one week. All abnormal blood pressure results will be communicated to the clinic director at each site who will be an integral part of triage and ensuring follow up. Any change in medication management or observation of an alert value will be communicated from the nurse as soon as possible. The prevention nurse will then generate a note to be entered into the electronic medical record and will communicate directly with the subject's PCP. The research nurses will be integrated parts of their respective health clinic.

Medication adverse effects, including kidney and electrolyte imbalances: All participants who are prescribed a clinically indicated new medication according the nurse-managed protocol will have that medication prescribed by the participant's usual health care provider, who will take primary responsibility for counseling the patient about side-effects and ordering follow-up laboratories. In addition, each participant will be counseled by the prevention nurse about

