possible side effects and need for any monitoring. These protocols therefore will provide an additional level of monitoring compared to routine clinical care.

Anti-hypertensive medication: Any patient prescribed an ACE-inhibitor, angiotensin receptor blocker, diuretic, or aldosterone antagonist, will be asked to return in 7-10 days for a repeat chemistry panel to check kidney function and electrolytes. The blood pressure algorithm will have special recommendations for those with more advanced chronic kidney disease (eGFR <60). Providers caring for study participants with conditions including but not limited to CKD and ASCVD, will be permitted to take their patients off of any protocolized management. Providers will take primary responsibility for the prescription of any medications in this study.

Lipid lowering medication: When a new lipid-lowering agent is prescribed, the prevention nurse will call 2 weeks after initiation to discuss adherence and any possible side-effects. The nurse will use an evidence-based approach to evaluation and management of muscle symptoms and other intolerances of statins as recommended by NLA guidelines. This will include ordering of creatinine kinase levels or liver function tests when appropriate.

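### For alert blood pressures without acute symptoms, one sentence gives the medication decision to the study team, while the rest of the protocol gives it to the responsible provider; its high trigger is also narrower than the alert definition

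*Combined protocol and SAP*

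**What the plan says.** The rule in question is in Protections against risk, Blood Pressure. It covers people in the intervention arm "whose average SBP > 180 and DBP > 110 or SBP < 90 or DBP < 40 but are without acute symptoms". For them the "primary provider will be notified and medications will be changed as deemed appropriate by the study team".

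The intervention description in section 8, Aim 2 Procedures, assigns the decision differently:

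- Component 1 (care coordination): "The prevention nurse will direct subsequent management decisions to the designated provider".
- Component 2 (nurse-managed medication protocols): the nurse uses the algorithms to form recommendations and approaches the designated responsible provider for prescriptions. "The responsible provider will ultimately decide on final management decisions", and that provider "may request to have the participant be taken OFF management protocols as clinically indicated".

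The safety text adds two statements about prescribing:

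- Potential risks, Other medication side effects: protocol medications are only recommended by the nurse and "must ultimately be prescribed by the subject's treating provider according to his/her best clinical judgement and approval".
- Protections against risk, Anti-hypertensive medication: "Providers will take primary responsibility for the prescription of any medications in this study".

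On thresholds, the Blood Pressure paragraph first defines a high alert as an average SBP above 180 and/or DBP above 110, at a study visit or at home. Such a value "will be considered an alert value and will trigger assessment by the clinician". The sentence on symptoms of acute end-organ damage uses the same and/or. Only the no-symptom sentence uses a plain 'and'.

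**The concern.** Two parts of the protocol answer the same question differently. When an intervention participant has an alert average and no acute symptoms, the safety sentence has the provider notified and the study team judge what change is appropriate. The intervention description has the team recommend and the provider decide. Site staff acting on a very high or very low pressure need to know whose decision counts. With the present wording, each side could think the other holds the decision, or both could change the regimen.

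The trigger has its own defect. A participant with only one of the two high thresholds exceeded meets the alert definition, yet the sentence that says what to do in the absence of symptoms does not reach that participant.

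**Working it through.** No calculation applies: the point depends on no sample size, power or error rate. The check sets the texts side by side.

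**Step 1. Who decides?**

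| Place in the protocol | Role of the study team or nurse | Role of the provider |
|---|---|---|
| Protections against risk, Blood Pressure (no-symptom sentence) | Judges which medication change is appropriate | Is notified |
| Aim 2, Component 1 | Directs management decisions to the designated provider | Receives them |
| Aim 2, Component 2 | Recommends, then approaches the provider for prescriptions | Makes the final decision; may take the participant off the management protocols |
| Potential risks, Other medication side effects | Only recommends | Prescribes on own judgement and approval |
| Protections against risk, Anti-hypertensive medication | Not addressed | Carries primary responsibility for prescribing any study medication |

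The first row differs from the next three on who judges the change. The last row concerns prescribing and is compatible with the first.

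**Step 2. Is an exception stated?** Component 2 states its rule without exempting alert values. The no-symptom sentence does not say that it overrides Component 2. The paragraph directly after it, on medication adverse effects, returns to new protocol medication being prescribed by the participant's usual provider.

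**Step 3. Do the terms match?** The no-symptom sentence speaks of the primary provider and the study team. Components 1 and 2 speak of a designated, responsible provider, who may be the HIV provider, the PCP or a non-HIV specialist. The sentence does not say whether its primary provider is that same person.

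**Step 4. Which high values does each sentence cover?**

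| Average reading | Alert definition (and/or) | Acute-symptom sentence (and/or) | No-symptom sentence (and) |
|---|---|---|---|
| SBP >180 and DBP >110 | covered | covered | covered |
| SBP >180 only | covered | covered | not covered |
| DBP >110 only | covered | covered | not covered |

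The low limits (SBP <90 or DBP <40) are joined by 'or' in both the alert definition and the no-symptom sentence, so the mismatch is confined to the high side.

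**Step 5. What still applies to the uncovered values?** Potential risks, Detection of clinically significant problems, lists each threshold separately and has any value that reaches one reported to the care provider. The alert definition still triggers clinician assessment. Abnormal results still go to the clinic director, and the nurse still records an alert value and communicates with the PCP.

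**The case against.** The strongest reply is that the no-symptom sentence is itself the exception: a specific safety pathway for extreme values. Component 2 sits within a routine algorithm triggered at home averages above 130/90. A specific rule can displace a general one, so pointing to the lack of a stated exception is partly circular. This is arguable, and it is why the confidence is medium. It does not remove the problem, because nothing in the sentence tells a site to read it that way.

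A second reply is that the team judges and the provider prescribes. That fits the Anti-hypertensive medication paragraph. It does not fit Component 2, which is about deciding, or the Other medication side effects paragraph, which calls for the provider's own judgement and approval.

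A third reply is that the study team includes physicians. The Blood Pressure paragraph does designate infectious disease physicians among the investigators as each site's clinical contact. It does not give them the medication decision, and on this reading the decision still leaves the responsible provider.

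On the trigger, one can say that 'and' was meant loosely, as a list of alert types. That is plausible and supports correcting the word.

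A reader might infer that the study nurse may prescribe for these participants, or that they are left without medical cover. The documents support neither. Prescribing stays with providers throughout. Clinician assessment, triage by JNC 8 recommendations, the clinic director's role, follow-up contact within one week and communication with the PCP surround the sentence. None of these steps, however, says who decides the medication change.

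**Conclusion.** The inconsistency is real and minor. The no-symptom sentence and the provider-decides rule (Components 1 and 2, supported by the Other medication side effects paragraph) name different decision-makers for the same participants and the same act. The sentence's high trigger is also narrower than the alert definition in its own paragraph. The conclusion assumes that 'study team' carries its ordinary meaning and that an exception to Component 2 would have to be stated. If the sponsor intended a separate safety pathway, the defect is only that the protocol does not say so.

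No frequency is attached. The plan gives neither a diastolic distribution nor a rate of alert home readings, and a count of alert readings would not measure how often anyone is unsure who decides.

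A reader might go further and infer a bias in the 12-month systolic comparison, because the sentence applies only to the intervention group. That does not follow from this wording: the defect concerns who authorises a change, and no effect on the estimate is claimed.

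**What to change.** In Protections against risk, Blood Pressure, make two edits to the no-symptom sentence:

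1. Replace the clause on notification and medication change with: *the designated responsible provider will be notified, the study team may recommend a medication change, and that provider will decide and prescribe.*
2. Change the high trigger to *SBP > 180 and/or DBP > 110*, matching the alert definition and the acute-symptom sentence.

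If the sponsor does want the study team to be able to act urgently at these values, state that as an explicit exception to Component 2 and name the physician role that holds the authority.

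The cost is a short protocol modification, IRB review and a notice to site staff. It needs no new visits or data fields and no change to the analysis.
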